### 265 6.2 Data Analysis and Interpretation

Values are presented as mean (SD), median (IQR) or number (%), unless stated otherwise. All analyses are performed by intention-to-treat, and all patients who have available CGM data are 268 included in the primary analysis and all secondary analyses unless otherwise noted. All efficacy 269 outcomes and continuous glucose monitoring based outcomes are summarized and analyzed using 270 the intervention period and intention-to-treat analysis set, and safety analyses included all data up to 271 the end of the study. The primary and secondary outcomes are compared between the two groups 272 with a linear mixed-effect regression model. Missing data are not imputed. The noninferiority 273 hypothesis is tested for the primary outcome by estimating the difference in the percentage of sensor 274 glucose measurement in TIR between the iNCDSS group and the physician group, and the lower limit of 95% CI of -6.0% is estimated as the noninferiority threshold. The proportion of participants 275 276 with events (capillary glucose concentrations <3.0 mmol/L, <2.2 mmol/L, >20.0mmol/L, and/or 277 ketoacidosis) in each group is compared with Fisher's exact test. Compliance is calculated as the 278 percentage of the number of insulin orders where dosages are actually ordered according to 279 iNCDSS recommendation against the total number of insulin orders. All statistical analyses are 280 performed with the use of SAS 9.3 software and R software.

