## 129 **3.4 Study Procedure**

- 130 The study consists of the following periods: 1) a screening period before admission (<2 weeks); 2) a
- run-in period on the first day of hospitalization; and 3) a 5-days intervention period duringhospitalization (Figure 1).
  - **Screening Period Run-in Period** Intervention Period ----- <2 weeks 1 day 5 days ----iNCDSS treatment (intervention group) Reassess for eligibility Obtain informed Physician reassess the patient to continue consent and screen and start initial cycle of for eligibility insulin regimen treating or discharge Senior physician treatment (control group) Figure 1. Flow chart

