## 142 **3.4.2 Run-in period**

- 143 The first day of hospitalization is the run-in period. Patients are reassessed for eligibility with regard
- to HbA1c results. Height, body weight, HbA1c level, and previous diabetes treatments are recorded. In the run-in period, the initial insulin regimen and dose are determined by the physician based on guidelines and patient's disease status. The iNCDSS system fetches the patient's clinical information and initial insulin regimen and dosage and then recommends the next insulin dose. All obligatory assessments should be completed in this period. The data obtained from clinical
- evaluation and laboratory tests for screening are used for baseline assessment as well. After the
- run-in period, subjects will be randomly assigned to the intervention group and the control group at
- 151 1:1 ratio.

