### 215 **4.2 Recording and Reporting of Adverse Events**

- All non-serious and serious adverse events will be collected from the time of signature of informed consent until the end of the trial and recorded in the case report form. The occurrence time, clinical manifestation, treatment, duration, and outcome should be recorded in detail in the case report form. If an abnormal laboratory examination occurs, the patient should be followed up until the results of the examination return to normal, or to the level before treatment, or to determine if it is not related to the treatment.
- If severe adverse events occur in participants, physicians should immediately provide the appropriate care to ensure their safety. Additionally, physicians will report the adverse events and

treatment to the Principal Investigator and the Committee within 24 hours and complete the report

225 form.

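### Section 6.2 makes available CGM data a condition for secondary outcomes that do not come from the sensor, and leaves the hypoglycaemia and hyperglycaemia comparisons with two possible populations

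*Protocol*

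**What the plan says.** All references are to the Protocol.

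- **Population, section 6.2.** The governing sentence reads in part "analyses are performed by intention-to-treat, and all patients who have available CGM data are" "included in the primary analysis and all secondary analyses unless otherwise noted". Missing data are not imputed.
- **Efficacy window, section 6.2.** Efficacy and CGM-based outcomes use "the intervention period and intention-to-treat analysis set".
- **Safety window, section 6.2.** The same sentence continues that "safety analyses included all data up to" the end of the study. It gives an end but neither a start nor a population.
- **Secondary outcomes, section 3.5.2.** Items 1 to 7 are sensor measures. Item 8 is capillary glucose from SMBG, item 9 hypoglycaemia events, item 10 hyperglycaemic events and item 11 mean total daily insulin dose.
- **Event definitions, sections 4.1.1 and 4.1.2.** Hypoglycaemia is defined on capillary glucose or, if severe, also by need for assistance. Acute hyperglycaemic complications are defined on capillary glucose, ketoacidosis or hyperosmotic status. Neither definition uses the sensor.
- **Collection of events, section 4.2.** "All non-serious and serious adverse events will be collected from the time of signature of informed consent until the end of the trial".
- **Timeline, sections 3.4 and 3.4.2.** There is "a screening period before admission (<2 weeks"), and then "The first day of hospitalization is the run-in period". During the run-in a physician sets the initial regimen for every patient. Randomisation follows the run-in.

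**The concern.** Availability of CGM data is known only after randomisation. Using it as an entry condition is unavoidable for time in range and the other sensor measures, because nothing can be computed without the sensor. It serves no purpose for capillary glucose, insulin dose or clinical events, which are recorded separately. Section 3.1 says that CGM data are read retrospectively and do not influence treatment, so a failed or lost sensor does not by itself mean that the other records are missing.

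Two things are at stake. First, usable data from randomised patients would be discarded, so the comparison would no longer be the intention-to-treat comparison that the protocol promises. Second, the hypoglycaemia and hyperglycaemia comparisons could be run on either of two denominators, each with support in the text. Safety is a stated objective (section 2), so that choice should not be left open until the data are seen.

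A smaller point concerns the same sentences. Because the safety data have no stated start and events are collected from consent, nothing in the protocol keeps events from before randomisation out of the between-arm test.

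**Working it through.** **1. Which outcomes the CGM condition reaches**

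| Outcome (section 3.5.2) | Needs the sensor? | Exception noted in 6.2? | Population as written |
|---|---|---|---|
| 1–7 sensor measures | Yes | Not needed | CGM subset |
| 8 capillary glucose means | No | None | CGM subset |
| 9 hypoglycaemia events | No | Unclear: safety clause says all data | CGM subset or all patients |
| 10 hyperglycaemic events | No | Unclear: safety clause says all data | CGM subset or all patients |
| 11 total daily insulin dose | No | None | CGM subset |

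For items 8 and 11 the plain reading excludes patients without CGM data. For items 9 and 10 the safety clause might be the noted exception, but it sets a time limit and names no population.

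**2. Possible size**

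The denominator is the planned total of 142, which reproduces. With margin 6 points, SD 12 points, one-sided alpha 0.025 and 80% power, the normal approximation gives 63 per arm, and 126/0.9 = 140. The t-based calculation gives 64 per arm, and 128/0.9 = 142.2. The sample size itself is not in question here.

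The documents give no rate of missing CGM data. Assuming 5% to 10%:

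- 142 × 0.05 = 7.1, about 7 patients
- 142 × 0.10 = 14.2, about 14 patients

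The planned dropout of about 10% in section 6.1 is not an estimate of this rate, because the protocol does not equate dropout with having no sensor data.

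**3. The safety window (secondary point)**

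If safety data ran from consent, time before randomisation would be up to about 14 + 1 = 15 days against 5 randomised days, or 15/20 = 75%. Counting hospital days only, it is 1/6 = 17%. The second figure is the more realistic for the capillary events that are tested, because the screening section describes no capillary testing.

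To see what inclusion would do, let p be the risk after randomisation and q a common risk before it. The counted risk is 1 − (1 − p)(1 − q), and the risk difference shrinks by the factor (1 − q). All risks below are assumptions: p = 15% versus 5%, 71 per arm, Fisher's exact test, two-sided 0.05.

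| q | Counted risks | Difference (points) | Risk ratio | Power |
|---|---|---|---|---|
| 0 | 15.0% vs 5.0% | 10.0 | 3.0 | 41% |
| 1% | 15.9% vs 6.0% | 9.9 | 2.7 | 38% |
| 2% | 16.7% vs 6.9% | 9.8 | 2.4 | 35% |
| 5% | 19.3% vs 9.8% | 9.5 | 2.0 | 29% |
| 10% | 23.5% vs 14.5% | 9.0 | 1.6 | 22% |

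The risk ratio and power fall, while the absolute difference moves little. The formula is the same whichever arm has the higher risk, so the effect is dilution in either direction. Power is only 41% even with no events before randomisation.

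**The case against.** **The safety sentence may already be the exception.** Section 6.2 allows for exceptions, treats safety separately, speaks of all data, and compares events by group. On that reading items 9 and 10 already use everyone. This is a fair reading, and it is why the event outcomes are called contradictory rather than wrongly restricted. It does not help items 8 and 11, for which no exception appears.

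**A SAP may define the safety set and the start of the event window.** That is so, and the SAP is not shown. The objection carries most weight for the window, where the protocol is silent on the start. It carries less for the population, where the protocol states a rule and the rule is too broad.

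**The window point rests on inference.** This stands in part. Section 4.2 says when events are collected, not which are compared, and collecting from consent is proper. Section 6.2 gives only an end. A reader might infer that up to two weeks of screening events will be counted against the arms, but the documents do not say so. Screening comes before admission and describes no capillary testing. Acute complications such as ketoacidosis are exclusions, and eligibility is reassessed on the run-in day. The realistic source is mainly that one day.

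**The capillary means have a window.** Correct: section 2.2 fixes them to the 5-day trial period. Only their population is at issue.

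**A reader might infer that both features make the new system look safer than it is.** The documents do not support this. Events before randomisation are equal in expectation between arms and would hide a benefit as readily as a harm. As for the CGM condition, section 4.3 does describe withdrawal after certain events when the expert committee does not endorse the iNCDSS regimen. But such a patient may have sensor data up to that point and so still qualify, and nothing in the documents links sensor loss to events or to one arm.

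**Conclusion.** The population point holds. As written, section 6.2 removes randomised patients without CGM data from the capillary glucose and insulin dose comparisons, and it leaves the hypoglycaemia and hyperglycaemia comparisons with two defensible populations. Both conflict with the stated intention-to-treat principle. The size is unknown: about 7 to 14 of 142 patients if 5–10% lack CGM data, which is an assumption. The direction of any bias cannot be stated.

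The window point is secondary: it is an unstated start that should be closed in the same edit. Its effect would be dilution, and the power figures above only illustrate it under assumed risks. The documents do not support the reading that safety is definitely analysed from consent, or that either feature favours the iNCDSS arm.

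This is a cheap improvement to the wording. It does not affect the primary analysis.

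**What to change.** In section 6.2:

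1. Confine the CGM-data condition to the primary outcome and the sensor-derived secondary outcomes (items 1 to 7 of section 3.5.2).
2. State that capillary glucose, hypoglycaemia events, hyperglycaemic events, total daily insulin dose and adverse events are analysed in all randomised patients, by assigned group, whether or not CGM data are available.
3. State that the between-arm Fisher comparison counts events from randomisation to the end of the study, and that earlier events are listed separately. Collection from consent in section 4.2 stays as it is.

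The cost is about two sentences, with no new data and no change to the sample size. The one drawback is that sensor and non-sensor outcomes will have slightly different denominators, so each table should show its own number of patients.

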### 193 **4.1.1 Hypoglycemia**

- 194 We determine the number of patients with hypoglycemia as defined by the Joint Position Statement
- 195 of the American Diabetes Association and the European Association for the Study of Diabetes.
- 196 Minor hypoglycemia is defined as a recorded capillary blood glucose level <3.9 mmol/L, which the
- 197 patient has been able to self-treat. Clinical significant hypoglycemia is defined as a recorded
- 198 capillary blood glucose level <3.0 mmol/L. Severe hypoglycemia events are defined as a capillary
- $199 \qquad \text{glucose level} < 2.2 \text{ mmol/L or an episode that requires of assistance of another person due to severe}$
- 200 impairment in consciousness or behavior.

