### 201 4.1.2 Acute hyperglycemia complications of type 2 diabetes

202 Capillary blood glucose >20.0 mmol/L, and/or ketoacidosis, and/or hyperosmotic status.

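### The safety events compared in Protocol 6.2 do not match the definitions in 4.1.1 and 4.1.2, so some events the trial itself calls severe are tested at a lower level or not at all

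*Protocol*

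**What the plan says.** Three parts of the Protocol bear on this.

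- **Section 4.1.1** sets three levels of hypoglycaemia. Minor is a capillary value <3.9 mmol/L with the condition that the "patient has been able to self-treat". Clinically significant is <3.0 mmol/L. Severe is <2.2 mmol/L "or an episode that requires of assistance of another person due to severe" impairment of consciousness or behaviour. The section states that patients with hypoglycaemia are counted under these definitions.
- **Section 4.1.2** defines acute hyperglycaemia complications as "Capillary blood glucose >20.0 mmol/L, and/or ketoacidosis, and/or hyperosmotic status".
- **Section 6.2** gives the only event comparison with stated criteria: Fisher's exact test on the proportion of participants "with events (capillary glucose concentrations <3.0 mmol/L, <2.2 mmol/L, >20.0mmol/L, and/or" ketoacidosis.

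Section 3.5.2 also lists the incidence of hypoglycaemic and of hyperglycaemic events as secondary outcomes 9 and 10, with no threshold attached to either.

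**The concern.** Safety is part of the stated study objective (section 2), and the Fisher comparison is where the Protocol says which participants count as having a safety event. Two elements of the definitions in section 4.1 are missing from that list: the assistance criterion for severe hypoglycaemia, and hyperosmotic status. Both are clinical criteria that do not depend on a glucose threshold. Section 4.3 treats coma from low glucose and hypertonic coma as events that end a patient's participation, so the Protocol plainly regards clinical events of this kind as grave.

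An analyst who follows 6.2 literally would therefore report a severe-event comparison that differs from the one 4.1 describes. Two analysts working from the two sections could report different counts from the same data.

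**Working it through.** The documents give no event rates, so there is no figure to reproduce. The total of 142 in section 6.1 is sized on time in range and does not enter here. The check is to pass the same events through both sets of rules.

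**Rules applied**

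- 4.1.1: minor if glucose <3.9 and self-treated; clinically significant if <3.0; severe if <2.2 or assistance needed for severe impairment.
- 6.2: one row for <3.0 and one for <2.2.

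**Hypoglycaemia** (example values in mmol/L)

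| Event | Under 4.1.1 | Under 6.2 | Result |
|---|---|---|---|
| 2.0, assistance for severe impairment | clinically significant, severe | <3.0 and <2.2 | agrees |
| 2.5, assistance for severe impairment | clinically significant, severe | <3.0 only | counted, but not as severe |
| 3.4, assistance for severe impairment | severe | none | lost |
| No capillary value, assistance for severe impairment | severe | none | lost |

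For severe hypoglycaemia, then, the sections agree below 2.2, disagree on level at 2.2-2.9, and disagree on whether the event counts at all from 3.0 upwards or where no value was recorded.

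**Hyperosmotic status**

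| Event | Under 4.1.2 | Under 6.2 | Result |
|---|---|---|---|
| With capillary glucose >20.0 | yes | yes, by glucose | agrees |
| With ketoacidosis | yes | yes, by ketoacidosis | agrees |
| With neither | yes | none | lost |

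**Secondary point: 3.0-3.8 mmol/L without severe impairment**

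This question lies inside 4.1.1 and is not produced by 6.2. The self-treatment condition can be read in two ways.

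| Event at 3.4, no severe impairment | Condition read as the act of self-treating | Condition read as the ability to self-treat |
|---|---|---|
| Patient treats it | minor | minor |
| Staff treat it, patient was able to | no category | minor |
| Staff treat it, patient was not able to | no category | no category |

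The middle row changes with the reading. It is a foreseeable case here: the trial runs on hospital wards (3.1), where nurses give the insulin (3.4.3.1). Below 3.0 mmol/L the ambiguity leaves no event unclassified, because the clinically significant level depends on glucose alone.

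**The case against.** The strongest reply is that little is really lost. Section 4.1.1 commits the trial to counting patients under its full definitions. Section 4.2 records every adverse event with its manifestation and treatment, and 6.2 bases the safety analyses on all data to the end of the study. Most of this stands: the events will be on record, which is why the repair is cheap. But recording an event does not decide whether the participant counts in the between-group comparison, and outcomes 9 and 10 have no threshold that would decide it. Nor is the 6.2 list easily read as shorthand for 4.1. It names one clinical event, ketoacidosis, so omitting the other two cannot be put down to listing glucose thresholds only.

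A reader might infer more than the documents support:

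- **That assistance-requiring hypoglycaemia and hyperosmotic state are simply not counted.** The tables show otherwise. Assistance episodes below 3.0 mmol/L enter the <3.0 row, those below 2.2 also enter the <2.2 row, and hyperosmotic cases with glucose >20.0 mmol/L or ketoacidosis are included.
- **That every nurse-treated 3.0-3.8 mmol/L event falls outside the definitions.** This holds only if the condition means the act of self-treating.
- **That mild hypoglycaemia goes uncompared.** The Fisher list has no <3.9 row, but sensor time at 3.0-3.8 mmol/L is secondary outcome 3 and hypoglycaemic events are outcome 9. Section 6.2 compares secondary outcomes between groups. Outcome 3 measures time rather than patients with events, but it covers this band whoever gives treatment.
- **That overlapping levels are an error.** The thresholds are nested, and testing nested thresholds is legitimate.
- **That the limited power of Fisher's test at this sample size measures the defect, or that the plan would take a non-significant result as equal safety.** The power would be much the same with a corrected list, and any power figure needs assumed event rates. The Protocol claims non-inferiority for time in range only.

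**Conclusion.** The mismatch is real and internal to the Protocol: 6.2 leaves out one criterion of 4.1.1 and one of 4.1.2. Its reach is limited to three groups: assistance-requiring episodes at 2.2-2.9 mmol/L (counted at a lower level), assistance-requiring episodes at 3.0 mmol/L or above or without a capillary value (lost), and hyperosmotic status with neither glucose >20.0 mmol/L nor ketoacidosis (lost). How many participants that means cannot be estimated from the documents. No stated number changes, and the primary non-inferiority analysis is unaffected.

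The conclusion assumes that the 6.2 list is applied literally. A statistical analysis plan that is not shown might settle the matter, but it would have to depart from one of the two sections. The self-treatment wording is an ambiguity to clear up, not a demonstrated gap. The correction should be made because safety is a stated objective and these are events the trial itself calls severe.

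**What to change.** 1. In 6.2, replace the event list with a reference to the definitions for analysis. Severe hypoglycaemia would be <2.2 mmol/L or assistance required for severe impairment (4.1.1). Acute hyperglycaemia would be >20.0 mmol/L and/or ketoacidosis and/or hyperosmotic status (4.1.2). The <3.0 mmol/L comparison stays as it is.
2. In 4.1.1, reconcile the self-treatment condition with the inpatient setting, so that it is clear how a staff-treated 3.0-3.8 mmol/L event without severe impairment is classified for analysis. Which reading was intended is for the investigators to state.

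The cost is a few lines of wording, settled before the data are analysed. Section 4.2 already puts the manifestation and treatment of each adverse event on the case report form, so no new data collection and no change in sample size is needed.

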#### 50 2. Study Objectives

The objective of the study is to evaluate the efficacy and safety of insulin dosage titration by the iNCDSS system as compared with senior physicians in glucose control in type 2 diabetic patients treated with subcutaneous insulin injection. We hypothesize that the glycemic control in type 2 diabetic patients receiving insulin dosage titrated according to the iNCDSS system recommendation is non-inferior to that in patients receiving insulin dosage titrated by senior physicians assessed by the percentage of time of sensor glucose concentration in the targeted range.

57 **2.1 Primary Objectives** 

58 To evaluate the effect of insulin dosage titration according to iNCDSS system on glucose control

- assessed by percentage of time of sensor glucose measurement in target range (TIR) of 3.9-10.0
- 60 mmol/L during the 5 days trial period as compared to senior physicians in type 2 diabetic patients

61 with insulin therapy.

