## 62 2.2 Secondary Objectives

- (1) To evaluate the effect of insulin dosage titration according to iNCDSS system on glucose
  control assessed by the percentage of time of sensor glucose concentration above range
  (10.1-13.9 mmol/L or >13.9 mmol/L) or below range (3.0-3.8 mmol/L or <3.0 mmol/L) during

  the 5 days trial period as compared to senior physicians in type 2 diabetic patients with insulin
  therapy.
- (2) To evaluate the effect of insulin dosage titration according to iNCDSS system on mean sensor
  glucose concentration, glucose management indicator (GMI), and glycemic variability (%CV)
  during the 5 days trial period as compared to senior physicians in type 2 diabetic patients with
  insulin therapy.
- 72 (3) To evaluate the effect of insulin dosage titration according to iNCDSS system on mean
   73 pre-meal and pre-bed capillary glucose concentration at each defined time during the 5 days
   74 trial period as compared to senior physicians in type 2 diabetic patients with insulin therapy.
- 75 (4) To evaluate the risk of hypoglycemia of insulin dosage titration according to iNCDSS system
   76 as compared to senior physicians in type 2 diabetic patients with insulin therapy.
- To compare the mean total daily insulin dose in type 2 diabetic patients receiving insulin
   titration by iNCDSS system and by senior physicians.

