## 79 3. Study Design

### 80 3.1 Design Overview

81 The study is a multicenter, patient-blind, and randomized controlled trial to evaluate the efficacy 82 and safety of iNCDSS in the clinical application. Eligible patients are randomly allocated into two 83 groups at a ratio of 1:1 after screening and run-in period. Randomization is stratified according to 84 sites and baseline HbA1c level. Patients in the intervention group receive insulin dosage titration set 85 by the iNCDSS assisted system and patients in the control group receive insulin dosage titration set 86 by senior physicians. A total of 142 type 2 diabetic patients will be enrolled and this study will be 87 conducted in the wards of Department of Endocrinology and Metabolism in Zhongshan Hospital, 88 Xuhui Central Hospital, and Shanghai Fifth People's Hospital, Fudan University. All patients are 89 studied for 5 consecutive days. Continuous glucose monitoring (CGM) is performed using flash 90 glucose monitoring (Abbott Freestyle Libre, USA) to measure the primary outcome of the 91 percentage of time of sensor glucose concentration in the target range during the 5 days trial period. 92 The CGM data will be analyzed retrospectively, and the treatment will not be influenced by data 93 gained by CGM. 94 **3.2 Study Population** 

- Eligible patients should meet the inclusion criteria and be excluded from the study if they meet anyof the exclusion criteria.
- 97 **3.2.1 Inclusion criteria**
- 98 Patients included in this study should meet the following criteria:
- 99 1) Patients with type 2 diabetes;
- 100 2) Aged  $\geq 18$  years old;
- 101 3) Treated with diet alone, any combination of oral antidiabetic agents, and/or insulin

therapy for at least 3 months;

103 4) HbA1c: 7.0%-11.0%.

104 **3.2.2 Exclusion criteria** 

- 105 Patients will be excluded from this study if they meet any of the following exclusion criteria:
- Acute diabetic complications including diabetic ketoacidosis or hyperglycemic
   hyperosmolar state;
- 108 2) BMI≥45 kg/m^2;
- 109 3) Women who are pregnant or breast-feeding;
- 110 4) Subjects with severe cardiac, hepatic, or renal diseases;
- 111 5) Subjects with any psychiatric or psychological diseases;
- 112 6) Subjects with severe oedema, infections, or peripheral circulation disorders;
- 113 7) Patients plan to receive surgery during hospitalization;
- 114 8) Subjects who cannot comply with the protocol.

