## 255 6 Statistical Analyses

## 256 6.1 Sample Size Estimate

257 The design of this study is a non-inferiority randomized clinical trial to explore the efficacy and 258 safety of the iNCDSS compared with senior physicians. The sample size calculation was based on 259 the primary outcome. According to our previous study, the proportion of time the sensor glucose 260 measurement in the target glucose range of 3.9-10.0 mmol/L during the intervention period was 261 80% with a standard deviation of 0.12. A margin of 6 percentage points was calculated to assess 262 non-inferiority in the difference in the TIR between the groups. We calculated that 142 patients 263 were needed (considering a dropout rate of approximately 10%) to achieve a power of 80% with an 264  $\alpha$  value of 0.025 (one-sided 95% CI).

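### The capillary-glucose and ketoacidosis events get a Fisher test but no risk difference or confidence interval, so the plan does not show how much excess risk remains possible

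*Protocol*

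**What the plan says.** Protocol section 2 states a double aim: "The objective of the study is to evaluate the efficacy and safety of insulin dosage titration" by iNCDSS as compared with senior physicians. Section 2.2 adds a secondary objective: "To evaluate the risk of hypoglycemia of insulin dosage titration according to iNCDSS system" against the same comparator. The non-inferiority hypothesis in section 2 concerns glycaemic control only; it "is non-inferior to that in patients receiving insulin dosage titrated by senior physicians assessed by the percentage of time of sensor glucose concentration", meaning TIR.

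Section 6.1 repeats the efficacy-and-safety aim, but "The sample size calculation was based on" the primary outcome, which is TIR. Section 3.1 sets the size: "A total of 142 type 2 diabetic patients will be enrolled", allocated 1:1.

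Section 6.2 treats the two halves of the aim differently. TIR gets an estimated between-group difference, a 95% CI and a limit of -6.0%. The event proportions (capillary glucose <3.0, <2.2 or >20.0 mmol/L, and/or ketoacidosis) get one method: the proportion with events "in each group is compared with Fisher's exact test". The section gives no risk difference, no interval and no statement of how a non-significant result will be described.

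**The concern.** A test of equality has two outcomes: a difference is shown, or it is not. Neither says how large an excess risk the data leave open, and that is what a safety comparison of a dosing system has to tell its readers. Because the trial was sized on TIR, the event comparison has whatever precision 142 patients happen to give. If the events are uncommon, a non-significant result is likely even when the risk under iNCDSS is two or three times that under physicians. The p-value alone would not reveal this; an interval would.

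**Working it through.** **Inputs.** From the Protocol: 142 patients, 1:1, so 71 per arm; about 10% dropout, so about 64 per arm (71 × 0.9 = 63.9); TIR SD 0.12; margin 0.06; one-sided alpha 0.025; power 80%. Assumed, because the protocol gives neither: the event rates, and a two-sided 5% level for Fisher's test.

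**The plan's own figure.** n per arm = 2 × (1.96 + 0.842)² × (0.12 / 0.06)² = 62.8, so 63 per arm and 126 in total; 126 / 0.9 = 140. With the t distribution, n = 63.8, so 64 per arm; 128 / 0.9 = 142.2. The stated 142 is reproduced, from TIR inputs only.

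**Power of the Fisher test.** For assumed risks p_C (physicians) and p_I (iNCDSS), power is the sum of Bin(a; n, p_I) × Bin(b; n, p_C) over all tables (a, b) with two-sided Fisher p ≤ 0.05.

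| Physicians vs iNCDSS (assumed) | 71 per arm | 64 per arm |
|---|---|---|
| 2% vs 4% | 1.8% | 1.3% |
| 5% vs 10% | 11.7% | 9.8% |
| 10% vs 20% | 31% | 27% |
| 15% vs 30% | 50% | 45% |
| 20% vs 40% | 69% | 63% |
| 2% vs 6% | 8.5% | 6.5% |
| 5% vs 15% | 41% | 36% |
| 8% vs 24% | 69% | 63% |
| 10% vs 30% | 82% | 77% |

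Power reaches 50% for a doubling at a control rate of about 15% (71 per arm) or 16% (64 per arm), and for a tripling at about 6% or 6.6%. Below those rates the increase is missed more often than not; above them it is not.

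**What an interval would add.** The Newcombe interval combines the two Wilson intervals. For 5/71 vs 0/71:
- The difference is 7.04 points. The Wilson limits are 3.05% to 15.45% for 5/71 and 0% to 5.13% for 0/71.
- Lower limit: 7.04 − √[(7.04 − 3.05)² + (5.13 − 0)²] = 7.04 − 6.50 = +0.5 points.
- Upper limit: 7.04 + √[(15.45 − 7.04)² + 0²] = 15.45, printed here as +15.4 (unrounded 15.449).

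| iNCDSS vs physicians, events of 71 | Fisher p | Newcombe 95% CI, points |
|---|---|---|
| 5 vs 0 | 0.058 | +0.5 to +15.4 |
| 3 vs 1 | 0.62 | −3.9 to +10.4 |
| 6 vs 2 | 0.27 | −2.6 to +14.7 |
| 9 vs 3 | 0.13 | −1.1 to +18.5 |

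The smallest splits with p ≤ 0.05 are 6 vs 0, 8 vs 1, 10 vs 2 and 11 vs 3. The three observed triplings in the table are all non-significant, and their intervals leave open excesses of roughly 10 to 19 points. With no events in one arm, the exact upper limit for that arm's risk is 1 − 0.025^(1/71) = 5.1%.

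**The case against.** The strongest reply is that nothing here is an error. Fisher's test suits sparse 2×2 tables. Sizing a trial on its primary outcome and comparing safety events without a margin is common, and section 6.1 says the trial is to explore efficacy and safety. Interval methods and zero-event handling are often left to a SAP, and nothing in section 6.2 forbids a risk difference. An interval also does not add information: with 6 vs 2 events the upper limit is still +14.7 points. Detecting 5% vs 10% with 80% power would take about 435 per arm, and 2% vs 6% about 376. The limit is the sample size, not the test.

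Most of that stands, and it rules out three stronger readings.

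- A reader might infer that the plan will treat a non-significant Fisher result as proof of safety. The protocol never says so, and it confines non-inferiority to TIR.
- A reader might infer that the whole safety assessment rests on this test. It does not. Sensor time below range is a secondary outcome (3.5.2) analysed by mixed model (6.2), all adverse events are collected (4.2), and an expert committee reviews them (4.3).
- A reader might infer that a doubling or tripling of serious events would generally be missed. The protocol gives no rates, and 10% vs 30% has 82% power. The tested events are glucose thresholds and/or ketoacidosis; severe adverse events are defined separately in 4.1.4.

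What does not stand is that the other measures fill the gap. Mean percentage of time below range is a different quantity from the proportion of patients with a capillary event, and event recording and committee review are monitoring, not between-group estimates. Section 6.2 does assign the linear mixed model to secondary outcomes in general, and event risk is listed among them in 3.5.2. But the sentence specific to these proportions names Fisher's test. The method is therefore fixed in the protocol rather than left open, and an exploratory safety aim is a reason to estimate rather than only to test.

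**Conclusion.** The point holds as a cheap improvement of minor severity. For the capillary-glucose and ketoacidosis events, the stated between-group method is a valid test that cannot bound an excess risk, in a trial that names safety as an objective and was sized on TIR alone. The size of the problem depends on event rates that the protocol does not give. At 71 per arm and a two-sided 5% level, a doubling is usually missed below a control rate of about 15%, and a tripling below about 6%. Above those rates the test performs better. The primary TIR analysis is unaffected.

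**What to change.** In section 6.2, for each event category:

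- Report the risk difference, iNCDSS minus physicians, with a two-sided 95% CI (Newcombe or Miettinen-Nurminen, with an implementation that handles zero events).
- Base the safety statement on the upper limit, that is, the largest excess risk the data do not exclude.
- State that a non-significant Fisher p-value is not evidence of equal safety. Fisher's p may stay as a descriptive result. Since p and interval can disagree, as at 5 vs 0, say that the interval carries the interpretation.

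The cost is one or two sentences and a few lines of code on data already collected, settled before unblinding. No margin and no added patients are needed. The downside is a more cautious safety statement: even 0/71 events leaves an upper limit of about 5.1% for that arm's risk. The interval displays the limited precision; it does not remove it.
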